5.2.3 Exploratory analyses

If appropriate, primary and secondary outcomes will be compared between subgroups of patients defined by median age, timing of treatment initiation (0 to 6 days, 7 to 30 days and \geq 31 days) and haemorrhage location (lobar versus non-lobar). For participants randomised to anticoagulants versus control, relevant subgroups also include CHA²DS²VASc score (median score as cut-off) and HAS-BLED score (median score as cut-off). The same statistical analyses as described above will be applied.

If low power, we will only present descriptive numbers and not statistical tests.

5.2.4 Hierarchical structure:

Since the study is multicentre, data might exhibit a hierarchical structure with some degree of cluster effect within study centres. The intra-class correlation coefficient (ICC) will be estimated to assess the possible cluster effect in all outcome variables. If ICC will show to be non-negligible suitable adjustment of statistical methods specified above will be applied through inclusion of random effects on study centre into the considered models. In such a

case, frailty models (Cox PH model with fixed and random effects) and generalized linear mixed models will be estimated instead of Cox PH model and ordinal regression model, respectively.

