2.3 Randomisation

All participants eligible for inclusion were randomised using a central, web-based randomisation system. Participants with an indication of antiplatelet drugs were randomised in the antiplatelet part of the trial, whereas participants with atrial fibrillation and an indication for anticoagulant drugs were randomised in the anticoagulant part of the trial. For each of these trial parts, participants were randomised to either intervention (treatment with antithrombotic drugs) or open control using a minimisation algorithm without a pre-determined sequence. The first participant was randomly allocated with a probability of 0.5 to one of the arms. Adaptive minimisation was used to allocate each subsequent participant with a probability of 0.8 to the arm that minimises the difference between the arms, with respect to baseline characteristics (see below) in the previously randomised participants. The minimisation criteria are listed below.

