2.3.1 Minimisation criteria in randomisation algorithm

- Age
 - o < 70 versus \geq 70 years
- Index sICH location
 - o Only supratentorial lobar regions are affected; yes versus no
- Probability of a good outcome at six months (10)
 - o < 0.15 versus \geq 0.15
- Days from index sICH to randomisation
 - o 0 to 6 days versus 7 to 30 days versus > 30 days
- Antiplatelet drug the patient's physician would use if allocated (this criterion only applies to the antiplatelet trial)
 - o Aspirin only; yes versus no

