2.4 Sample size

The sample size estimation was made before the initiation of the study. A fourfold increase in the annual rate of recurrent sICH on antithrombotic drugs (from 2% to 8%) was considered unacceptable and higher than any plausible beneficial effect antithrombotic drugs would have on ischaemic events.

With power of 80% and a 5% significance level to detect an increase of the annual rate of recurrent sICH from 2% to 8% with antithrombotic therapy, the sample size was estimated to 500 participants randomised to intervention versus control. The sample size estimation was made for the trial as a whole, and not as two separate trials investigating the effect and safety of antiplatelets and effect and safety of anticoagulants as two separate trials. No sample size estimation for the two separate trials was performed. Regardless of this, analyses will be made for antiplatelet treatment versus control and anticoagulant treatment versus control separately.

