4.4 Baseline patient characteristics

4.4.1 Baselines variables

The following baseline variables will be reported: Age, sex, comorbidities, living arrangements, functional status at randomisation, medications used before randomisation, physiological parameters, time from sICH to randomisation, location (non-lobar versus lobar) and volume (< 30 ml versus \geq 30 ml) of sICH on CT or MRI before randomisation.

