5.2.1 Primary analysis

Primary analysis is a comparison between groups of time-to-first event of new symptomatic sICH during two-year follow-up. This will be assessed by generating life tables, Kaplan-Meier curves and applying log-rank test.

The sample size calculation, performed before the study was started, is based on comparisons of proportions. However, in the protocol (latest protocol version v210421), time-to-event-analysis is defined as primary analysis. We will follow the protocol.

To adjust the differences between the groups, Cox proportional hazards (PH) regression model will be used. The results will be presented as an adjusted hazard ratio with the corresponding 95% CI.

All regression analyses will be adjusted for the variables being part of the minimisation criteria. If adjustment for all these variables is not possible due to few events (and consequently low power), age (< 70 versus \geq 70) and ICH location will be prioritized.

If the PH assumption is violated, time-dependent covariates will be included.

Since death is a competing risk, we will perform competing risk model as a sensitivity analysis.

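### The timing subgroup uses a start of treatment that open controls do not have, and no method is named to test whether the treatment effect differs between subgroups

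*SAP*

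**What the plan says.** SAP section 5.2.3 states that, if appropriate, "primary and secondary outcomes will be compared between subgroups of patients defined by median age, timing of treatment initiation" and by haemorrhage location. The timing bins are 0 to 6, 7 to 30 and at least 31 days. The anticoagulant part adds two risk scores split at the median. On method the section says only "The same statistical analyses as described above will be applied", followed by a fallback: "If low power, we will only present descriptive numbers and not statistical tests".

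Four other places bear on this:

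- Section 2.3: "participants were randomised to either intervention (treatment with antithrombotic drugs) or open control".
- Section 2.3.1 lists "Days from index sICH to randomisation" as a minimisation criterion, in bins of 0 to 6, 7 to 30 and more than 30 days.
- Section 4.4.1 lists "time from sICH to randomisation" among the baseline variables to be reported.
- Sections 5.2.1 and 5.2.2 define the analyses that 5.2.3 points back to: life tables, Kaplan-Meier curves, log-rank test, Cox regression, and ordinal logistic regression for the modified Rankin Scale. On covariates: "All regression analyses will be adjusted for the variables being part of the minimisation criteria".

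**The concern.** There are two separate problems.

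**The timing variable.** A subgroup for a randomised comparison has to be defined in both arms and fixed before allocation. Start of treatment is neither. A participant allocated to open control has no start date, and in the treated arm the start comes after randomisation. Taken at its word, the rule leaves every control unclassified, so not even a descriptive table by arm can be built from it.

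**The contrast.** Comparing outcomes between subgroups says which kind of patient has more events. It does not say whether treatment works differently in them. None of the analyses referred to has a term for that. The text does not prescribe a separate p-value in each subgroup, but it leaves that reading open. Under that reading, a significant result in one subgroup and not in the other can be taken for effect modification when the effect is the same in both.

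**Working it through.** **Timing variable: sections side by side**

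| | Section 5.2.3 subgroup | Section 2.3.1 minimisation factor |
|---|---|---|
| Clock stops at | start of treatment | randomisation |
| Bins (days) | 0-6, 7-30, ≥31 | 0-6, 7-30, >30 |
| Defined in controls | no | yes |
| Known before allocation | no | yes |

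In whole days the bins are identical. The minimisation factor is also a reported baseline variable (4.4.1). That it was the intended variable is an inference, but a strong one. No size can be put on this part, because the SAP does not state the delay from randomisation to first treatment.

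**Contrast: is there an interaction term anywhere?** The log-rank test compares two curves. The Cox and ordinal models carry the minimisation variables as covariates, that is, as main effects. The time-dependent covariates in 5.2.1 are a remedy for non-proportional hazards, and the random effects in 5.2.4 are for centre. None is a treatment-by-subgroup term.

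**What within-subgroup testing would do**

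Inputs from the SAP: 2% and 8% per year and 500 participants (2.4); two-sided 5% (3.2); two years (5.2.1). Assumptions: 2% v 4% as a smaller effect; 250 and 200 participants in one part; two equal halves; equal arms; the same true effect in both halves; death and loss to follow-up ignored. The figure of 500 is an upper bound, since it was planned for the whole trial and the two parts are analysed separately (5.2).

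Two-year risks: 1 − 0.98² = 0.0396; 1 − 0.96² = 0.0784; 1 − 0.92² = 0.1536.

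Power in one half, with n per arm of 125, 62.5 or 50: p = Φ[(d − 1.96·s₀)/s₁], where d is the risk difference, s₀ the pooled and s₁ the unpooled standard error. For 2% v 8% and n = 125: d = 0.1140, s₀ = 0.0374, s₁ = 0.0367, so p = 0.867.

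Chance that exactly one half reaches p<0.05: 2p(1 − p).

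| Annual rates | Participants | p per half | Exactly one half significant | Log-rank simulation (6,000 runs) |
|---|---|---|---|---|
| 2% v 8% | 500 / 250 / 200 | 0.867 / 0.580 / 0.488 | 23% / 49% / 50% | 20% / 48% / 50% |
| 2% v 4% | 500 / 250 / 200 | 0.255 / 0.148 / 0.127 | 38% / 25% / 22% | 38% / 24% / 21% |
| no effect | any | 0.05 | 2 × 0.05 × 0.95 = 9.5% | 7-8% |

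With equal effects, a 5% interaction test gave a false signal in 0.1% to 3.7% of 20,000 simulated runs. It falls below 5% because events are few and runs with an empty cell were counted as not significant.

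**What an interaction analysis can and cannot deliver**

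The standard error of the log ratio of two subgroup hazard ratios, with equal halves, is √[4(1/e_c + 1/e_t)], where e_c and e_t are the total events in each arm.

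| Annual rates | Participants | e_c, e_t | SE | 95% CI factor, exp(1.96·SE) |
|---|---|---|---|---|
| 2% v 8% | 500 | 9.9, 38.4 | 0.713 | 4.0 |
| 2% v 8% | 250 | 4.95, 19.2 | 1.008 | 7.2 |
| 2% v 4% | 500 | 9.9, 19.6 | 0.780 | 4.6 |
| 2% v 4% | 250 | 4.95, 9.8 | 1.103 | 8.7 |

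If the true hazard ratio is about 1 in one half and about 4 in the other, simulated interaction power is about 36%, 10% and 5% for 500, 250 and 200 participants.

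For the three-level timing subgroup, assume controls split equally. One level has no sICH event with probability q = 0.9604^(controls/3), and at least one level is empty with probability 1 − (1 − q)³. This gives 10%, 46% and 59% for 500, 250 and 200 participants. The hazard ratio for an empty level cannot be estimated.

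**The case against.** The case for leaving this alone has four parts.

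- **The label is a slip that the SAP nearly corrects itself.** An analyst unable to place controls would turn to the minimisation factor with the same bins, and the protocol, not shown here, may define the subgroup. That is plausible, but as written the SAP names the wrong variable, and it would permit classifying treated participants by their actual start date.
- **The missing interaction term is silence, not error.** Cox and ordinal models can carry such a term, and within-subgroup p-values are not prescribed. This stands in part: the harm quantified above arises only if tests are run within subgroups. But the stated contrast, outcomes between subgroups, does not address effect modification either.
- **The descriptive fallback removes most of the harm.** At 250 or 200 participants, power per half is 0.58 or less, so the SAP might run no tests. This is the strongest point, and it limits the weight of the finding. However, low power is given no threshold, the secondary composites may have more events than sICH alone, and the fallback does not repair the timing label.
- **An interaction test will rarely detect anything.** This is true, as the power figures show. It argues for reporting estimates with intervals and a caution, not for leaving the contrast undefined. Section 5.2.1 also allows adjustment to shrink to age and location when events are few, so a three-level timing interaction may not be fittable for sICH.

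**Conclusion.** Both parts hold. The timing subgroup is wrong as written: it is undefined for controls and arises after randomisation in the treated arm. The method named for the subgroups does not assess whether the treatment effect differs between them.

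If within-subgroup tests were used, a discordant pair of results under an identical effect would occur with a chance of roughly 20% to 50% where treatment has an effect, and somewhat under 10% where it has none. These figures rest on the assumed part sizes, equal halves and no competing death. The 2% v 8% scenario is the large end of the effect range, being the harm that section 2.4 treats as unacceptable: "A fourfold increase in the annual rate of recurrent sICH on antithrombotic drugs (from 2% to 8%) was considered unacceptable".

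The consequence is confined to exploratory analyses that apply only if appropriate and may be purely descriptive. The primary and secondary analyses are not touched. The text should be corrected because the error is plain and the correction costs almost nothing.

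**What to change.** In section 5.2.3:

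1. Replace the timing label with the minimisation factor "Days from index sICH to randomisation", using the bins in section 2.3.1.
2. State that, for each subgroup variable, treatment-versus-control estimates with 95% confidence intervals will come from the Cox or ordinal model with the subgroup main effect and a treatment-by-subgroup interaction, and that no significance claims will be made for individual subgroups.
3. Keep the descriptive fallback. Add that where a level has no events in an arm, so that the interaction cannot be estimated, only event counts by arm will be shown. This is a minimum trigger and does not narrow the existing low-power rule.
4. State that interaction power is low and that a non-significant interaction is not evidence of equal effects.

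The cost is one label and two or three sentences. No new data are needed: the timing variable is in the randomisation data and is already a planned covariate, though not one of the two given priority when events are few. The price is wide intervals and, for the three-level timing subgroup, a real chance that only counts can be reported for sICH.

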5.2.5 Quality control

Prior to statistical analysis a thorough quality check of the data base will be performed and obvious mistakes properly handled.

5.3 Missing data

During the study period, comprehensive efforts will be made to obtain complete outcome data. In case of missing values, different approaches will be considered to handle them, such as complete case analysis, multiple imputation or inverse probability weighting. Thorough sensitivity analyses will be performed in the case of imputation.

5.4 Statistical software

We plan to use the statistical software STATA version 17 or a more recent version.

